8.4.4 Site Close Out Visit

Conducted to ensure all study and regulatory-related activities have been completed prior to site closure.

8.5 Data Management

CRFs will be used at all investigational sites. All study data will be entered into commercially available web-based EDC. Data entry will be performed by the study site personnel. The EDC system requires no on-site software installation or specific hardware to operate. Investigators, clinical coordinators, data managers, and Penumbra clinical personnel will access project information and study data centrally via a web browser.

Automated data quality checks will display warnings for invalid data. Additionally, manual review of data listings may be used to identify data discrepancies or inconsistencies. The study site may be queried for clarification concerning CRF discrepancies or inconsistencies identified. If CRF corrections are necessary, they will be made by the Investigator or an authorized member of the Investigator's staff that is delegated to complete data entry (e.g. CRF/EDC). Questions or problems with submitted data will be addressed with the Principal Investigator via an electronic querying system, or through direct contact. The Investigator will review the CRFs for completeness and accuracy and provide his/her electronic signature and date to CRFs as evidence thereof. Any data items that have been changed will require reapplication of the electronic signature.

Study personnel will have individual login and password to access the clinical study information based upon each individual's roles and responsibilities. The application provides hierarchical user permission data entry, viewing, and reporting options.

All data entry and data update information, including the date and person performing the action, will be available via the audit trail, which is part of the EDC system.

All CRFs and data files will be secured to ensure confidentiality. Investigators are required to maintain source documents required by the protocol, including but not limited to laboratory results, reports, supporting medical records, and Informed Consent Forms. The source documents will be used during the regular monitoring visits to verify information entered on the CRFs.

9. Ethical Requirements

9.1 Declaration of Helsinki

The study will be performed in accordance with the applicable aspects of I.S. EN ISO 14155:2011, recommendations guiding physicians in biomedical research involving human subjects adopted by the 18th World Medical Assembly, Helsinki, Finland (1964 and later revisions), ICH and US FDA GCP guidelines.

It is the responsibility of the Investigator to obtain approval of the study protocol from the Institutional Review Board (IRB) and to keep the IRB informed of any serious adverse event, serious adverse device effects, and amendments to the protocol. All correspondence with the IRB should be filed by the Investigator and copies sent to the Sponsor or its designee.

9.2 Informed Consent

The Investigator is responsible for ensuring that a completed informed consent is obtained in accordance with Section 6.5 of this protocol, as delegated by the site-specific Delegation of Authority, and according to country and local requirements.

9.3 Subject Data Protection

Each subject will be assigned a unique subject identification number at the time of enrollment. This subject identification number will be retained throughout the study. Study sites will keep a log that notes the subject's name and corresponding subject identification number. All CRFs will be tracked, evaluated, and stored using only the subject ID number. No personal identifying information will be included on the CRFs.

The informed consent form will notify subjects that study monitors, Sponsor's representatives, auditors, and representatives of government agencies and ethics committees will have access to personal identifying information to ensure that data reported on the CRFs corresponds to the person who signed the consent form and the information contained in the source documentation.

10. Statistical Procedures

10.1 General Statistical Considerations

All confidence intervals presented will be two-sided. All statistical tests will be two-tailed with a significance level of 0.05. Descriptive statistics will be provided. This includes the number of observations, mean, median, standard deviation, inter-quartile range, minimum

and maximum for continuous variables and counts and percentages for discrete variables. Analyses will be conducted using SAS (SAS Institute, Cary, NC). The specific details of the planned analyses are described completely in the statistical analysis plan.

10.2 Sample Size Estimation for the Primary Outcome

The sample size calculations assume that 6.1% (22/360) of the study subjects experience a primary safety event as compared to 6.1% (272/4454) of the TOTAL trial high thrombus burden subset.²⁹ Based on a binomial analysis with a non-inferiority margin of 10%, a study of 360 Indigo System subjects will have 99% power with a one-sided alpha of 0.025. The sample size was adjusted to 400 subjects to account for up to 10% attrition rate.

10.3 Control of Systematic Error and Bias

The study will be conducted under a common protocol for each Investigational Site with the intention of pooling the data for analysis. Every effort will be made to promote consistency in study execution at each Investigational Site.

10.4 Missing Data and Imputation Methods

Every effort will be made to keep all missing data, particularly the 30-day outcomes, to a minimum. Some data may be missing, mainly due to lost-to-follow-up (LTFU) subjects. The primary analysis will be data as observed. Sensitivity analysis will be performed.

10.5 Definition of Populations

10.5.1 Screened

Screened patients are all patients considered for participation in the study, whether or not they sign informed consent.

10.5.2 Screen Failure

Screen failure patient are all patients considered for participation in the study, who failed to meet inclusion criteria or met exclusion criteria. Patients can be screen failed based on general or imaging criteria. These patients may or may not have signed an informed consent form.

10.5.3 Enrolled

An eligible patient is considered enrolled when the Indigo CAT RX Aspiration Catheter enters the body and informed consent is obtained (whichever is later).

10.5.4 Completed

Completed subjects are all subjects who were enrolled and completed the study follow-up or were known to have died prior to the follow-up timepoint are considered completed. The completed subject metric will be provided for 180-day follow-up.

10.5.5 Early Termination

Early termination subjects are all subjects who were enrolled but did not complete follow-up and were not known to have died. The early termination subject metric will be provided for 180-day follow-up.

10.6 Definition of Analysis Populations

10.6.1 Intent to Treat Sample

As the primary analysis, all performance and safety outcome measures will be analyzed under the intent-to-treat (ITT) principle. Under this principle, the ITT sample includes all subjects who are enrolled. This population is the primary analysis population.

10.7 Interim Analysis

No interim analyses are planned for the purpose of terminating the study for a positive result. No adjustments will be made to the confidence bounds for the final analysis.

10.8 Statistical Analysis of Primary Endpoint

The primary endpoint is the 30-day composite endpoint. The primary effectiveness analysis will be the difference between the study group and the historical control rate of 6% observed in the TOTAL trial high thrombus burden subset.

The null hypothesis is that the difference between the composite endpoint rate and the historical control at 30 days is greater than or equal to 10%. The alternative hypothesis is the difference at 30 days is less than 10%. Formally, the null and alternative hypotheses to be tested are as follows:

H₀:
$$P_{study} - 0.06 \ge 0.10$$

H_A: $P_{study} - 0.06 < 0.10$

Where P_{study} is the proportion of patient experiencing a composite endpoint event at 30-day follow-up visit.

Statistical analysis of the primary endpoint will be conducted using a binomial comparison to test the one-sided null hypothesis that the difference in proportions is less than or equal to 0.10.

The primary safety endpoint is met if the upper limit of the 95% confidence interval of the composite primary endpoint rate is less than 16% at a one-sided alpha of 0.025. The primary analysis will be unadjusted.

10.9 Secondary Statistical Analysis

The secondary performance and safety endpoints will be assessed via proportions based on the endpoint criteria and 95% confidence intervals will be presented. The Imaging Core Lab data supersede the investigator-reported data in all analyses of imaging-based endpoints. Survival estimates will also be utilized to evaluate the time-to-event using Kaplan-Meier methodology for events through 180 days. With the date of procedure set at day 0, any event occurring on or before day 180 will be included.

10.10 Analysis of Adverse Events

All adverse events will be summarized by showing the number and percent of subjects which report the event. Events will also be reported by relationship to the procedure or device. Adverse events judged as probably or definitely related to the Indigo® Aspiration System will be analyzed as device-related. The IMR data will supersede the investigator-reported data in all analyses of adverse events.

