4.2.2 Secondary Endpoints

Performance:

- 1. Final TIMI Flow Grade
- 2. Final TIMI Thrombus Grade
- 3. Myocardial Blush Grade
- 4. Distal Embolization Rate
- 5. Stent thrombosis at 180 days

Safety:

- 1. Stroke within 30 days
- 2. Major bleeding within 30 days
- 3. All-cause mortality within 180 days
- 4. Cardiovascular (CV) death within 180 days
- 5. Recurrent MI within 180 days
- 6. Cardiogenic shock within 180 days
- 7. Class IV heart failure within 180 days
- 8. Incidence of device related SAE(s)

5. Study Population

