7.6.3 Relationship to the Study Device

General adverse event and serious adverse event definitions can be found in Section 16 - Appendix I. A (S)AE is considered to be device-related when it is reasonable to believe that the event may have been caused by or is related to the study device. The following definitions will be used to assess the relationship of the adverse event to the use of study device.

- **Definite:** The temporal sequence is relevant and the event abates upon study device application completion/removal, or reappearance of the event on repeat study device application.
- **Probable:** The temporal sequence is relevant or the AE abates upon study device application completion/removal or the AE cannot be reasonably explained by the subject's condition or comorbidities. The AE is related or most likely associated with the study device.
- **Possible:** The temporal sequence between the study device and the AE is such that the relationship is not unlikely or there is no contradicting evidence that can reasonably explain the subject's condition. There is a possibility of a relationship between the AE and the study device.
- **Unrelated:** The AE is not associated with the device. There is no relation between the AE and the study device.

Similar grading will be used for assessing the relationship to index procedure/index coronary vessel occlusion.

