7	' Statistical Analysis				
7	.1	Primary Endpoint Analysis6			
7	7.2 Secondary Endpoint Analysis				
7	.3	Analysis of Adverse Events7			
8	Subgroup Analysis7				
9	9 Pooling Across Centers				
10	10 Lost to Follow-Up and Missing Data8				
11	11 Reviewers and Core Lab8				
1	11.1 Independent Medical Reviewer (IMR)8				
1	11.2 Imaging Core Lab9				
12		Changes to Planned Analyses9			
13	3 References				
14		Revision History			

1 Overview

The objective of the CHEETAH study is to demonstrate the safety and performance of the Indigo[®] Aspiration System using the CAT RX Aspiration Catheter in a population presenting with acute high thrombus burden coronary vessel occlusion who are referred for Percutaneous Coronary Intervention (PCI). Patients will be enrolled who meet the inclusion and none of the exclusion criteria, who (or Legally Authorized Representative, LAR) consent to participate, and in whom the study device has been inserted.

The study allows for enrollment of up to 400 subjects at up to 25 sites in the United States. Each site will be limited to a maximum enrollment of approximately 80 patients (~20% of total enrollment).

The primary endpoint of the study is the composite of cardiovascular (CV) death, recurrent Myocardial Infarction (MI), cardiogenic shock, or new or worsening New York Heart Association (NYHA) Class IV heart failure, within 30 days. Secondary endpoints of the study are as following:

Performance:

- 1. Final TIMI Flow Grade
- 2. Final TIMI Thrombus Grade
- 3. Myocardial Blush Grade
- 4. Distal Embolization Rate
- 5. Stent thrombosis at 180 days

Safety:

- 1. Stroke within 30 days
- 2. Major bleeding within 30 days
- 3. All-cause mortality within 180 days
- 4. Cardiovascular (CV) death within 180 days
- 5. Recurrent MI within 180 days
- 6. Cardiogenic shock within 180 days
- 7. NYHA Class IV heart failure within 180 days
- 8. Incidence of device-related SAE(s)

This Statistical Analysis Plan (SAP) will provide details to further elaborate statistical methods as outlined in the protocol and will describe analysis conventions. The SAP will be approved prior to database lock.

2 Sample Size for the Primary Outcome

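### The device-related SAE endpoint counts only probable and definite events, although the protocol's own definition of device-related also covers the grade Possible

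*Combined protocol and SAP*

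**What the plan says.** **Definition.** Protocol 7.6.3 (Relationship to the Study Device) treats an (S)AE as "device-related when it is reasonable to believe that the event may have been caused by or is related to the study device". It then sets four grades: Definite, Probable, Possible and Unrelated. The Possible entry ends "There is a possibility of a relationship between the AE and the study device". The Unrelated entry ends "There is no relation between the AE and the study device". The section adds that similar grading applies to the relationship with the index procedure.

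**Counting rule.** Protocol 10.10 (Analysis of Adverse Events) says: "Adverse events judged as probably or definitely related to the Indigo® Aspiration System will be analyzed as device-related". SAP 7.3 repeats this and applies the same two-grade cut-off to procedure-related events. Both documents let the Independent Medical Reviewer (IMR) override the investigator, and both plan summaries of all adverse events and reporting by relationship.

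**Endpoint.** Incidence of device-related SAEs is the eighth secondary safety endpoint in protocol 4.2.2 and in SAP Section 1. Under protocol 10.9 and SAP 7.2, secondary endpoints are "assessed via proportions based on the endpoint criteria and 95% confidence intervals will be presented".

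**The concern.** The same term has two meanings. Under 7.6.3 an SAE graded Possible is device-related. Under 10.10 and SAP 7.3 it is not. Neither document explains the narrower rule, and neither plans a version of the endpoint that includes the excluded grade. Protocol 7.6.1 also uses the term for 72-hour reporting to the database, so one event could be device-related when it is reported and not when it is analyzed.

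The study has a single arm, so no concurrent control can show an excess of events. The primary composite in 4.2.1 counts events whatever their cause. The device-related SAE rate is the listed endpoint that attributes harm to the catheter. A discrepancy that can only lower that rate should be removed, even if its effect turns out to be small.

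**Working it through.** The plan states no expected rate or count for this endpoint, so there is no figure to reproduce. The check is a comparison of texts, followed by what they imply for the count.

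**Step 1: where each grade falls.**

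| Grade in 7.6.3 | Within the 7.6.3 definition? | Counted under 10.10 and SAP 7.3? |
|---|---|---|
| Definite | yes | yes |
| Probable | yes | yes |
| Possible | yes, on its wording | no |
| Unrelated | no | no |

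Section 7.6.3 does not say outright which grades meet its definition, so the Possible row is a reading. It is hard to read otherwise. The definition asks only whether the device may have been the cause, the Possible entry affirms that it may have been, and Unrelated is the only grade that denies a link.

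**Step 2: look for a reconciling rule.** Protocol 10.9 and SAP 7.2 set the form of the estimate, not the grades counted. IMR override changes who assigns the grade, not which grades count. The by-relationship reporting in 10.10 and SAP 7.3 does not specify a row for Possible. The sensitivity analyses in SAP Section 10 concern missing primary outcomes only.

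**Step 3: direction and size.** Let N be the number of subjects, k those with at least one probable or definite SAE, and m those whose highest-graded SAE is Possible.

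- Planned rate = k/N
- Rate under 7.6.3 = (k + m)/N
- Difference = m/N, which is never negative

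With N = 400, the planned enrollment, each such subject adds 1/400 = 0.25 percentage points. If m = 0 the two rates agree.

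**Step 4: illustration only.** The documents give neither k nor m, so every count below is an assumption. The plan names no interval method. Exact (Clopper-Pearson) limits are used here: lower = 0.025 quantile of Beta(x, N − x + 1), with 0 if x = 0; upper = 0.975 quantile of Beta(x + 1, N − x).

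| k | m | Planned k/400 (95% CI) | Inclusive (k + m)/400 (95% CI) |
|---|---|---|---|
| 0 | 4 | 0.0% (0 to 0.9%) | 1.0% (0.3 to 2.5%) |
| 2 | 4 | 0.5% (0.1 to 1.8%) | 1.5% (0.6 to 3.2%) |
| 4 | 0 | 1.0% (0.3 to 2.5%) | 1.0% (0.3 to 2.5%) |
| 4 | 4 | 1.0% (0.3 to 2.5%) | 2.0% (0.9 to 3.9%) |
| 4 | 8 | 1.0% (0.3 to 2.5%) | 3.0% (1.6 to 5.2%) |

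The table shows how the choice of rule can matter. It does not predict that it will.

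**The case against.** The best defence is that the cut-off is deliberate. Protocol and SAP state the same rule, and the SAP revision history records that definitions of device- and procedure-related events were added on purpose. Section 7.6.3 sits among the investigator's reporting duties, where a broad definition is natural, while 10.10 is an analysis rule, where a narrower and more specific one can be reasonable. Counting every Possible event would charge some harm from PCI or from the infarct to the catheter. This stands as a reason to keep the narrower count visible. It does not explain why the plan uses one term for both meanings without saying so.

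It is also fair that Possible events are not lost. They stay in the overall AE and SAE tables, and stroke, major bleeding, death, recurrent MI, shock and Class IV heart failure are endpoints whatever the relatedness. What is missing is an explicit count and interval that includes Possible.

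A reader might infer three stronger things that the documents do not support.

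- **Irreversible harms are pushed out of the endpoint because they cannot abate.** Abatement on removal figures in Definite, but in Probable it is one of several alternatives joined by *or*. An irreversible event can be graded Probable, and Probable is counted.
- **Device and PCI harm usually cannot be separated, so Possible will be the commonest grade.** Protocol 6.7 requires angiograms after wire crossing, after aspiration and after PCI, and a core lab reads them, so many angiographic events can be timed to a step. No document gives the expected mix of grades.
- **The endpoint is understated by some known multiple.** Any ratio comes from assumed counts.

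**Conclusion.** The inconsistency is real and appears in both documents. Secondary safety endpoint 8, as planned, can fall below the rate that the protocol's own definition gives, and cannot exceed it. The shortfall is m/N, where m is unknown: 0.25 percentage points per affected subject at N = 400, and nothing if no subject has Possible as the highest SAE grade. The conclusion rests on reading Possible as within the 7.6.3 definition, which its wording supports.

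The consequence is limited. The endpoint is a descriptive proportion with an interval. The primary composite does not use relatedness, so its test, alpha, power and sample size do not change. The documents do not show that the safety result will be materially biased. They show a one-sided ambiguity in a named safety endpoint that can be settled cheaply in advance.

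**What to change.** Reconcile protocol 7.6.3 with protocol 10.10 and SAP 7.3. For endpoint 8, on IMR grading, pre-specify two lines, each with a 95% confidence interval:

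1. subjects with a definite, probable or possible device-related SAE (the 7.6.3 definition);
2. subjects with a definite or probable device-related SAE (the present rule).

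State which line is the headline. If it is the narrower one, give the reason. Report procedure-related events in SAP 7.3 the same way.

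The cost is about one sentence in each document and one extra table row for each type of relatedness. The grades are already collected, so no new data are needed. The downside is that the inclusive rate may be somewhat higher and less specific to the device, which is why both lines should be shown.

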10.11 Baseline Characteristics

Baseline data including, but not limited to, demographics, clinical characteristics, and angiographic characteristics will be summarized using descriptive statistics.

10.12 Pooling Across Centers

Analyses will be presented by treatment group using data pooled across sites. Adjusted analysis using key baseline variables and the study site will be used to assess any potential site effects. This analysis will be performed on the intent-to-treat population.

10.13 Final Report

A final report will be completed, even if the study is prematurely terminated. At the conclusion of the study, a multi-center abstract reporting the results will be prepared and may be presented at a major meeting(s). A multi-center publication may also be prepared for publication in a reputable scientific journal. The publication of results from any single center experience within the study is not allowed until the aggregate study results have been published, unless there is written consent from the Sponsor.

11. Study Committees and Core Labs

11.2 Independent Medical Reviewer

The Independent Medical Reviewer (IMR) will be an independent medical doctor(s) who does not participate in the study. There may be more than one IMR. The IMR is responsible for assisting in the development of specific criteria used for the categorization of clinical events and clinical endpoints in the study.

The IMR will review and adjudicate appropriate clinical events, mainly related to the device and study endpoints. A web-based electronic database will be provided to the IMR

for case review and adjudication. The designated Penumbra staff who are responsible for reviewing safety data on an ongoing basis will coordinate collection of information for the event dossier. Additional details related to the IMR are specified in the IMR Charter.

11.3 Imaging Core Lab

The Imaging Core Lab is composed of independent medical doctor(s) who are not participants in the study. The Imaging Core Lab is responsible for assisting in the development of specific criteria used for the categorization of clinical endpoints in the study. A web-based electronic database will be provided for the Imaging Core Lab to review and adjudicate images. Additional details related to the core lab are specified in the Imaging Core Lab Charter.

12. Study Administration

